1.3 Research Design and Methods

A. Research Procedures

Study Subjects

Participants will include school-aged children with ASD between the ages 5-12. We selected this age group because a diagnosis is typically made by the age of 5. This age group also allows us to profit from neuroplasticity while avoiding potential variables related to children undergoing puberty. This age group is also likely to be enrolled in intensive ABA programs aimed at executive functioning and social communication intervention. Based on the gender distribution of ASD in the population, we expect that our group will be approximately 75% male. Participants will be recruited from the local New Jersey community, from ABA schools and ABA agencies.

Experimental Design

The study will use a randomized double-blind controlled placebo (sham tDCS) crossover design. The study will involve 5 total months of participation. Participants will be randomized into two groups using a random number generator. They will receive either:

- A) 20 active tDCS stimulation followed by 20 sham stimulation: or
- B) 20 sham stimulation followed by 20 active tDCS stimulation.

Randomization & Blinding

We anticipate recruiting 24 participants in anticipation of 4 subjects dropping out. We will use SAS programming to generate a randomization schedule with a block length of 6 and four blocks. Participants will enter the randomization schedule after consent is obtained and they are assigned a study ID.

002	2	Sham	tDCS
003	2	Sham	tDCS
004	1	tDCS	Sham
005	2	Sham	tDCS
006	1	tDCS	Sham

Block 1 example- there will be four blocks = 24 participants recruited.

[figure not shown]
Subjects 21-24 (to account for drop outs) will receive randomization order of the subject they are replacing but will receive a new study ID. For example if the subject with study ID 004 drops out then subject with study ID0021 will receive randomization schedule 1.

[name] will utilize the generated randomization schedule to provide active tDCS and sham stimulation codes that will be entered into the tDCS device (by the parent) prior to each session. These numeric codes will be random numbers and not distinct to the study group assignment, protecting the blind. Because of her role, [name] will remain unblinded and will not be involved in any assessments. All other study staff, including Drs. [name], [name], and [name], will remain blind. Parents, participants, and ABA providers will also remain blind.

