Desensitization: Participants will be introduced to the tDCS equipment. Most participants may require desensitization to the tDCS equipment (see Potential Problem section) to the tDCS. Desensitization to the tDCS equipment will be provided by [name].

Baseline Assessment 1

- 1. Resting EEG
- 2. Parent completed questionnaires
 - a. Behavior Rating Inventory of Executive Function (BRIEF)

- b. The Pervasive Developmental Disorder Behavior Inventory (PDDBI)
- 3. ABA data for skills acquisition and target behavior for weeks 1-4
- 4. Randomizations to sham or tDCS

Phase A or B- Weeks 5-8

- 20 sessions of active or sham tDCS stimulation (depending on order assignment) five sessions per week
 - EEG resting EEG after tDCS #20

Weeks 5-8

- BRIEF, PDDBI,
- ABA data for skills acquisition and target behavior for weeks 5-8

Baseline 2: Washout and Crossover - Weeks 9- 12(subject continues ABA therapy)

- EEG before tDCS session end of week 12
- Weeks 9-12
- BRIEF, PDDBI end of week 12
- ABA data for skills acquisition and target behavior for weeks 9-12

Phase B or A - Weeks 13-16

20 sessions of active or sham tDCS stimulation (depending on order assignment)

Weeks 13-16

- Resting EEG after session #40 tDCS or sham BRIEF, PDDBI end of week 16
- o ABA data for skills acquisition and target behavior for weeks 13-16

Washout- Weeks 17-20 (subject continues ABA therapy)

- Resting EEG after week 20
- Weeks 17-20
- BRIEF, PDDBI week 20
- ABA data for skills acquisition and target behavior for weeks 17-20

Schedule of Measurements per Study Phase TABLE 2

Protocol Title: A Pilot Study of Transcranial Direct Current Stimulation in Children with ASD

PHASE	Enrollment	Baseline 1`	Phase A (active or sham)	Crossover/ Baseline 2	Phase B (active or sham)	Baseline 3
Time	Week 1-3	Week 4	Week 8	Week12	Week 16	Week 20
Consent	X					
Medical History	X					
Leiter-3*	X					
Vineland-III	X					
Caregiver tDCS training	X					
Desensitization	X					
Randomization	X					
BRIEF		X	X	X	X	X
PDDBI		X	Х	Х	Х	X
ABA program DTT data		X	Х	Х	Х	Х
EEG 2-5 min of continuous recording during rest.		Х	X	X	Х	Х

^{*}Completed for subjects that do not have a cognitive assessment within the past 3 years

B. Study Duration

Subjects will participate in the study for 20 weeks.

C. Endpoints:

20 sessions of active and sham tDCS stimulation

[figure not shown]

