1.6 Study Variables

Expiration Date:

Protocol Title: A Pilot Study of Transcranial Direct Current Stimulation in Children with ASD

A. Independent Variables, Interventions, or Predictor Variables

Subjects will continue to receive their ABA therapy provided by their regular therapist as standard of care. Subjects will be randomized to begin with either sham or tDCS treatment and then cross over to the other treatment arm. Each subject with receive tDCS or sham however the order will be different in the two groups. The active tDCS and sham are procedurally identical.

B. Dependent Variables or Outcome Measures:

AIM 1: The following data will be used as outcome measures at the end of each phase of the study.

Primary The use of rating scales, completed by parents and teachers, measuring overt behavior is an often used and well-established method for assessing various domains of social, emotional, and behavioral functioning and treatment outcomes. As we are targeting the prefrontal areas, the primary outcome measure will be the **Behavior Rating Inventory of Executive Function (BRIEF)**, a test that has normative data for children aged 2 to 90 years. It has parent versions containing 63 (preschool age) 86 (school age) items, taking approximately 10 to 15 minutes to complete. Each item score is converted within each scale for computation of T scores. The BRIEF contains eight subdomains of executive function: 1) Inhibit, 2) Shift, and 3) Emotional Control subdomains together result in an additional composite Behavioral Regulation Index (BRI). The subdomains 4) Initiate, 5) Working Memory, 6) Plan/Organize, 7) Organization of Materials, and 8) Monitor provide a composite Metacognition Index. The BRI and MI are also combined to obtain an overall Global Executive Composite (GEC).

Secondary

Our secondary outcome measure will be the **Pervasive Developmental Disorder Behavior Inventory (PDDBI)** and the Discrete Trial Training (DTT) data from the participant's ABA programs.

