1.8 Specimen Collection N/A

1.9 Data Collection

A. Primary Data Collection- all data will be entered into a RedCap database using the participant study ID. No personal identifiers will be entered into the RedCap database.

AI: Descriptive Data

- Vineland Adaptive Behavior Scales Third edition (https://www.pearsonassessments.com ([name] [name], [name]). is a well validated assessment of the child's daily living skills. [name] (study psychologist) will use video-conferencing, using Q-Global On-Screen Administration (OSA) to guide the interview and score responses.as recommended by the American Psychological Association. The VABS-III is organized around four Behavioral Domains: Communication, Daily Living Skills, Socialization, and Motor Skills. The VABS-III will take approximately 60 minutes to complete. It will be completed one time during the study in the baseline 1 phase. The results will be entered into a Redcap database using the child's personal study ID. No personal identifiers will be recorded or stored
- ➤ Leiter 3- (https://www.wpspublish.com) (for those subjects without cognitive assessment in the past 3 years) The Leiter 3 will be performed by the [name]. in the research rooms in the Child Health Institute. The Leiter-3 is a standardized nonverbal test of intelligence and cognitive abilities appropriate for individuals between the ages of 3-75 years. The Leiter-3 has been shown to be appropriate for individuals with autism and severe cognitive delays

A2: Primary Outcome Date (see section 1.6B for further information on these questionnaires)

➤ PDDBI- [name], and [name] (https://www.wpspublish.com) a link will be sent via email for the parent /caregiver to complete the PDDBI rating scale. The parent will complete the questionnaire 5 times during the study. It takes 15 min to complete.

➤ BRIEF -[name], [name], [name], and [name]- (https://www.parinc.com) a link will be sent via email for the parent /caregiver to complete the PDDBI rating scale. The parent will complete the questionnaire 5 times during the study. It takes 30 minutes to complete.

B. Secondary Data Collection

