6.0 Data Management Plan

6.1 Data Analysis

Analysis of the data in this study will follow the approach described in Wellek, S., and M. Blettner (2012). The following steps are required:

1. Baseline analysis to check the assumption of negligible carryover effects. This test has to be performed like an ordinary unpaired t-test

- .2. Test for differences between treatment effects. Formally, this test is carried out according to the same scheme as the pre-test. The crucial difference is that the customary formula for the unpaired t-test are now applied to the within-subject differences
- 3. Significance decisions: The significance of the difference between two treatments (tDCS and sham) is determined as well as the significance of carryover effects (step 1).

These steps are described in more detail below.

Baseline Analysis

For descriptive purposes, summary statistics of the demographic and outcome variables will be calculated. To ensure pre-stimulation (i.e., baseline) equivalence between participants assigned to the two treatment orders (i.e., sham-active vs. active-sham), the outcome measures obtained during the first baseline period (first baseline assessment session) between these groups will be compared using independent *t*-test comparisons. The primary dependent variable will be the BRIEF; fixed factors will be the treatment order (active-sham versus sham-active), and treatment condition (active and sham condition) and the secondary dependent variable will be the PDDBI. We note that, as described previously, the BRIEF will be used to assess executive functioning and the PDDBI is used to differentiate ASD from other conditions as well as to assesses the effectiveness of treatments in terms of Response to Interventions (RTI). The goal of this baseline assessment is to establish the equivalence of the two groups prior to intervention on the basis of the two outcome assessments.

In addition to summary statistics for the baseline assessments, nonlinear EEG features will be computed before testing for all subjects. Machine learning classifiers will be used to demonstrate that the two groups are equivalent and cannot be distinguished based on nonlinear EEG analysis (see [name] et al., 2018).

Hypothesis Testing

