As described briefly above, an unpaired t-test is applied to the within-subject differences for the outcomes of interest. We note that two summary outcome scores can be used (BRIEF and PDDBI), as well as for subscores. Because the subscores and the total scores are not independent, a Bonferroni correction is likely too strict and not warranted. Total scores and subcategory scores on each assessment will be tested for significant changes over time. The dependent or outcomes to be measured for within-subject differences within each group assignment (or treatment order: active-sham versus sham-active), treatment condition (active versus sham), and time (baseline and 4-week follow-up) will be the dependent variables. Independent variables will be group assignment, treatment condition, and time. The differences over time in either active or sham condition will be carried out using independent measures ANOVA. For all analyses, *P* values less than 0.05 will be considered statistically significant. Analyses were completed using standard R software.

EEG as a Biomarker for Treatment Outcome

The signal or time series from each sensor will be decomposed into multiple frequency bands using a wavelet transform (Walker, 2008). We note that the Haar wavelet transform yields a multiscale decomposition that is mathematically equivalent to the coarse-graining procedure first introduced by (Costa, Goldberger, & Peng, 2005) for multiscale entropy analysis of biological signals. The use of wavelets for multiscale signal decomposition and relationship of scale to traditional EEG frequency bands is discussed in ([name] et al., 2018). Using the wavelet transform, each sensor signal will be decomposed into power-of-two frequency bands that are approximately equal to the commonly used definitions of delta, theta, alpha, beta, gamma, and gamma+ bands used for EEG analysis. The specific software used for the wavelet transform is publicly available, along with instructions and python code, at: https://pywavelets.readthedocs.io.

Several nonlinear values will be computed on multiple scales for every sensor, including sample entropy, Lyapunov exponents, detrended fluctuation analysis (DFA), and correlation dimension (CD). These will be computed on multiple scales using publicly available software "Nonlinear measures for dynamical systems" or nolds, version 0.3.2, which can be downloaded from (https://pypi.python.org/pypi/nolds).

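### The primary BRIEF contrast is undefined, the wording leans towards change-from-baseline scores and an independent-measures ANOVA, and the pre-phase baselines are not used as covariates

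*Combined protocol and SAP*

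**What the plan says.** Section 1.3 sets the design: "The study will use a randomized double-blind controlled placebo (sham tDCS) crossover design". In section 1.6 "the primary outcome measure will be the Behavior Rating Inventory of Executive Function (BRIEF"), and of the Aim 1 outcomes it says "The following data will be used as outcome measures at the end of each phase of the study". Section 1.9 says of the BRIEF, as of the PDDBI, "The parent will complete the questionnaire 5 times during the study". Table 2 places these ratings at weeks 4, 8, 12, 16 and 20, and the timeline in section 1.3 confirms the second baseline: "BRIEF, PDDBI end of week 12".

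For the treatment comparison, section 6.1 (Hypothesis Testing) states that "an unpaired t-test is applied to the within-subject differences for the outcomes of interest". The same paragraph adds "Total scores and subcategory scores on each assessment will be tested for significant changes over time", gives a time factor with the levels baseline and four-week follow-up, and assigns differences over time under each condition to an ANOVA for independent measures. The independent variables listed are order group, condition and time. The Baseline Analysis paragraph of section 6.1 says "fixed factors will be the treatment order (active-sham versus sham-active), and treatment condition (active and sham condition"). Period appears in neither list.

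The first baseline is used to compare the two order groups. The week-12 rating has no stated role in the treatment test, and no baseline is named as a covariate.

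**The concern.** Two statisticians following section 6.1 could compute different primary results. One would subtract end-of-phase scores. The other would subtract changes from baseline, which brings in the noise of two more parent ratings. With 20 completers, precision is scarce, and the pilot's stated purpose (section 1.5) is to gather outcome data that could justify a powered trial.

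The ANOVA wording carries a separate risk. Taken literally, it treats a child's active and sham scores as if they came from different children, so it discards the advantage of the crossover. It also has no term for period, although ABA continues throughout and a drift between the phases is plausible.

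**Working it through.** **Inputs.** BRIEF at weeks 4, 8, 12 and 16 (Table 2). 20 completers (section 4.3), taken as 10 per order because the example block in section 1.3 has three of each. Alpha 0.05 (section 6.1), taken as two-sided. The documents give no SD, effect size, power or within-child correlation, so there is no planned figure to reproduce beyond 20 + 4 = 24 recruited. Everything below rests on assumed correlations, equal variances and normal data.

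**1. Three contrasts.** Let D = week 8 − week 16 (outcomes), B = week 4 − week 12 (baselines), and r = corr(D, B). Variance of the treatment estimate relative to D alone:
- end-of-phase scores: 1
- change scores (D − B): 1 + 1 − 2r = 2(1 − r)
- D adjusted for B: (1 − r²)(n − 3)/(n − 4) = (1 − r²) × 17/16 at n = 20

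The ratio of change to adjusted is 32/[17(1 + r)]. It exceeds 1 unless r is above 15/17 = 0.88.

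**2. Plausible r.** With equal correlation among the four ratings, cov(D, B) = 0, so r = 0. With serial correlation ρ per four-week step, Var(D) = Var(B) = 2(1 − ρ²) and cov(D, B) = ρ(1 − ρ²), so r = ρ/2. If only a share w of the within-child variance is serially correlated and the rest is rating error, r = wρ(1 − ρ²)/[2(1 − wρ²)].

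| Assumption | r | Change | Adjusted | Change ÷ adjusted |
|---|---|---|---|---|
| Equal correlation | 0 | 2.00 | 1.06 | 1.88 |
| ρ = 0.3 | 0.15 | 1.70 | 1.04 | 1.64 |
| ρ = 0.5 | 0.25 | 1.50 | 1.00 | 1.51 |
| ρ = 0.7 | 0.35 | 1.30 | 0.93 | 1.39 |
| ρ = 0.9 | 0.45 | 1.10 | 0.85 | 1.30 |
| ρ = 0.3, 40% rating error | 0.09 | 1.83 | 1.05 | 1.73 |
| ρ = 0.9, 40% rating error | 0.10 | 1.80 | 1.05 | 1.71 |

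**3. Power.** On 18 df, 80% power needs a noncentrality of 2.963. Doubling the variance gives 2.963/√2 = 2.095, which is 51%. At r = 0.4, change scores have 73% and the adjusted contrast (17 df) 84%. At r = 0, the adjusted contrast has 77%.

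**4. Break-even against end-of-phase scores.** (1 − r²) × 17/16 < 1 requires r² > 1/17, that is r > 0.24. With 20% rating error and ρ = 0.7, 0.8 and 0.9, the adjusted variance is 1.00, 1.00 and 1.02 times the unadjusted, so there is no gain.

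**5. Period.** An additive period effect adds the same constant to D in both orders and cancels when the orders are compared. In an example data set, the t-test on D and a model with child, period and treatment gave the same result (t = 2.3949, 18 df). Simulated power (n = 20, within-child correlation 0.7, treatment effect 0.5 SD):

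| Period effect | t-test on D | Paired, no period | Independent groups |
|---|---|---|---|
| 0 | 78% | 78% | 24% |
| 0.5 SD | 78% | 65% | 22% |
| 1 SD | 78% | 30% | 13% |

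The direction of subtraction matters. If the differences were coded active minus sham, an unpaired test between orders would test period: it rejected in 5% of simulations with a true 0.5 SD treatment effect, and in 78% with a pure 0.5 SD period effect.

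**6. Residual effect at week 12.** Suppose an effect λ of active stimulation in phase 1 remains at week 12. Then B differs by −λ between orders, and a covariate slope b shifts the treatment estimate by bλ/2. With b = 0.35 to 0.45 (ρ = 0.7 to 0.9), that is 0.18λ to 0.23λ. Change scores have b = 1, so the shift is 0.5λ.

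**The case against.** The strongest reply is that the plan may already be sound. Section 1.6 points to end-of-phase scores, and the cited crossover approach compares orders on within-child differences. Read as period 1 minus period 2, that test is valid and free of an additive period effect, and baseline adjustment is then largely a preference. This stands for that reading. A reader might infer from the factor lists that ABA-related improvement inflates the error of the primary t-test, or biases it when the orders are unequal in size. The documents do not support that: the effect cancels, and a simulated 13/7 split with period effects of 0, 1 and 3 SD showed no bias. Part of the factor wording sits in the Baseline Analysis paragraph, not with the test.

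Nor do the documents say outright that change scores are primary; the wording only leans that way. The four-week follow-up is itself ambiguous, because the design outline in section 1.3 places assessments after each washout, which could mean weeks 12 and 20. The variances above do not cover that reading. It adds to the case for a definition. The 80% starting point is only a yardstick, since section 1.5 sets no power target.

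Finally, week 12 follows the first phase, so adjusting for it admits any residual effect. That stands as a cost. The shift runs opposite to the bias from carryover still present at week 16, and is smaller with adjustment than with change scores.

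**Conclusion.** The point holds for the undefined difference, the lean towards change scores, the independent-measures ANOVA and the unused baselines. If change scores are meant, the treatment estimate has about 1.3 to 1.9 times the variance of the baseline-adjusted contrast (r from 0.45 down to 0). Relative to end-of-phase scores alone, the worst case considered is a doubling, or 80% power falling to 51%.

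It is tempting to conclude that ignoring the baselines always loses precision. That is not shown. Against end-of-phase scores alone, adjustment ranges from about 15% lower variance to 6% higher and helps only if r exceeds about 0.24. The documents give nothing from which to estimate r. The absence of a period term is a fault of the ANOVA and the factor list only. For an unpowered pilot this is a change that should be made, but it does not invalidate the design.

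**What to change.** In section 6.1, state the primary analysis as follows:
- **Contrast:** each child's end-of-phase BRIEF difference, period 1 minus period 2 (week 8 minus week 16), compared between order groups.
- **Covariate:** the baseline difference (week 4 minus week 12), prespecified.
- **Sensitivity analysis:** the unadjusted t-test on the same differences.
- **Removed from the primary role:** change-from-baseline comparisons.
- **ANOVA:** replace the independent-measures analysis with a within-child model that includes period and treatment.

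The cost is wording, one degree of freedom (17 instead of 18), and up to about 6% variance if the baselines carry no information. Any phase-1 effect remaining at week 12 enters the adjusted estimate, though less than with change scores. Setting the adjusted and unadjusted results side by side shows how far the adjustment moves the estimate. No new data are needed.

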Nonlinear values derived from Recurrence Quantitative Analysis (RQA) will be computed. RQA is an empirical approach to analyzing time series data that is in principle capable of characterizing all the essential dynamics of a complex system. It has been found to be useful for analyzing "real-world, noisy, high dimensional data" (Webber & Zbilut, 2005). Software for computing recurrence plot statistics is publicly available python package pyRQA 0.1.0 (Marwan, 2012). At least seven of the most commonly used recurrence plot values (RR, DET, LAM, L_max, L_entr, L_mean, and TT) will be computed and used in this study. These values have proven to be potential biomarkers for autism ([name] et al., 2018) and absence epilepsy ([name] et al., 2017) in our previous studies.

EEG analysis will first determine significant group differences between actual and sham tDCS for each of the nonlinear signal features computed. We hypothesize that significant changes will be observed in the nonlinear signal features. A Bonferroni correction will be required for the set of nonlinear measures. In addition to feature comparisons, regression models will be computed using the nonlinear EEG features as input variables and the change in assessment scores as output. Linear regression and machine learning regression models will be used.

Taken together, these analyses will provide the information necessary to determine if tDCS significantly improves the efficacy of behavioral therapy for improving cognitive function in children with ASD. In addition, the usefulness of EEG as a tool for measuring the changes in brain function due to tDCS augmented behavioral therapy will be determined.

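### No single BRIEF score or time point is named as primary, and up to 11 correlated BRIEF scores are each tested at 0.05 with no multiplicity rule

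*Combined protocol and SAP*

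**What the plan says.** Sections 1.6 B and 6.1 both give the BRIEF as primary without choosing a score. In 6.1 the wording is "The primary dependent variable will be the BRIEF". Section 1.6 B describes eight subscales, the Behavioral Regulation Index (BRI, three subscales), the Metacognition Index (MI, five subscales) and the Global Executive Composite (GEC), which combines the two indices. The GEC is described as overall but is not designated as the endpoint.

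Under Hypothesis Testing, section 6.1 says "We note that two summary outcome scores can be used (BRIEF and PDDBI), as well as for subscores" and then "Total scores and subcategory scores on each assessment will be tested for significant changes over time". It sets adjustment aside with "Because the subscores and the total scores are not independent, a Bonferroni correction is likely too strict and not warranted". For all analyses, P "values less than 0.05 will be considered statistically significant". No ordering, gatekeeping or exploratory label is given for the BRIEF scores. For the EEG features the same section takes the opposite line: "A Bonferroni correction will be required for the set of nonlinear measures".

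On timing, section 1.6 B places the outcome measures at the end of each phase, while section 6.1 refers to "time (baseline and 4-week follow-up) will be the dependent variables".

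**The concern.** The plan's premise is right, but its conclusion does not follow. Bonferroni is too strict for overlapping scores. That does not mean 11 tests at 0.05 behave like one test at 0.05. Unless one score is named in advance, a single subscale below 0.05 could be reported as a positive primary result while the overall composite shows nothing.

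This matters because section 6.1 calls for significance decisions ("The significance of the difference between two treatments (tDCS and sham) is determined") and ends by saying the analyses will settle whether tDCS significantly improves the efficacy of behavioral therapy. Results are to be published (section 6.4), and section 1.5 intends the outcome data to support a larger trial.

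The time point adds a second free choice. A four-week follow-up can mean the end of the four-week stimulation block or the visit after the four-week washout. The study schedule in section 1.3 lists assessments after each washout. The Research Timeline and Table 2 place the BRIEF at weeks 8 and 16 (end of stimulation) and at weeks 12 and 20 (end of washout).

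**Working it through.** The plan states no familywise error rate, so there is no figure of its own to reproduce. The check asks how often a trial with no treatment effect yields at least one significant BRIEF score.

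**Inputs from the documents**
- Scores: 8 subscales + BRI + MI + GEC = 11 (section 1.6 B).
- Test: unpaired t-test on within-subject differences between the two sequences (section 6.1).
- Threshold: 0.05 per test (section 6.1).
- Sample: 20 completers (section 4.3).

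**Assumptions**
- 10 completers per sequence and two-sided tests.
- One time point.
- Normal within-subject differences with a common correlation r between subscales. The documents give no correlations, so r = 0.3, 0.5, 0.7 and 0.8 are shown.
- BRI, MI and GEC are the means of 3, 5 and 8 subscales.

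**Formula.** For each score, t = (d̄₁ − d̄₂) / [s_p √(1/10 + 1/10)] with 10 + 10 − 2 = 18 degrees of freedom. The error rate is the share of null trials in which at least one eligible score has P<0.05.

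**Bounds.** Eleven independent tests would give 1 − 0.95¹¹ = 43.1%. One test gives 5%. Correlated scores fall between these.

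**Results** (400,000 null trials per column)

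| Scores that may count as primary | r=0.3 | r=0.5 | r=0.7 | r=0.8 |
|---|---|---|---|---|
| Any of 11 | 31.6% | 26.0% | 19.8% | 16.5% |
| 8 subscales and GEC only | 30.8% | 25.7% | 19.7% | 16.5% |
| BRI, MI or GEC | 9.3% | 8.2% | 7.2% | 6.8% |
| GEC alone | 5.0% | 5.0% | 4.9% | 5.0% |
| Any of 11, Bonferroni at 0.05/11 | 3.9% | 3.3% | 2.5% | 2.1% |

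The second row shows that the exact count of scores hardly matters. The last row confirms that Bonferroni is too strict here.

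**Does the GEC agree when a score is falsely significant?** Some score is significant and the GEC is not in 26.7% / 21.1% / 14.9% / 11.5% of all null trials. Divided by the first row, that is 84% / 81% / 75% / 70% of the false positives.

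**Sensitivity**
- A second run of 60,000 null trials per setting gave 31.6% / 26.1% / 19.9% / 16.4% for any of 11.
- 12 per sequence gave 31.4% / 26.0% / 19.7% / 16.4%; a 9/11 split gave 31.4% / 26.0% / 19.7% / 16.2%.
- At r = 0.9 the rate for any of 11 is still about 12.1%.

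The free choice of time point and the PDDBI scores are not counted in any of these figures.

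**The case against.** The strongest reply is that the plan never says one significant subscale makes the trial positive. Section 6.1 separates summary scores from subscores, and the GEC is the only overall BRIEF score described. On that reading the subscales are supportive and the error rate is 5%. The reading is reasonable, but the text says only that summary scores can be used, alongside subscores. That permits the GEC without designating it. The 16.5% to 31.6% range is therefore conditional on any score being allowed to count, and the composites-only figure of 6.8% to 9.3% belongs beside it.

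Other points have partial force:
- The correlations are assumed, and higher ones lower the figure. Even at 0.9, however, it is more than twice the nominal 5%.
- The 5% for the GEC presumes one deciding test. Section 6.1 also mentions an ANOVA, and section 1.9 lists the PDDBI under its primary outcome heading. Against that, step 2 of section 6.1 already makes the t-test the treatment comparison, and sections 1.6 B and 6.1 both call the PDDBI secondary.
- The EEG contrast is modest, since that analysis covers many features on multiple scales at 19 sensors. It shows that the authors recognise multiplicity, not that the two rules must match.
- The EEG text in section 1.3 lists a recording four weeks after treatment, separate from the end-of-treatment one. This favours the washout reading of the follow-up, but it concerns EEG only.
- Unadjusted subscale tests are common in pilots, and no go/no-go rule depends on them. That limits the consequence but does not answer the question of which score decides.
- The figure under section 1.3 C and some pages could not be read. The outcome and analysis sections are available.

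**Conclusion.** The concern holds. The plan fixes neither the BRIEF score nor the time point that decides the primary question. It tests all scores at 0.05 and rejects one correction without supplying another. If any of the 11 scores may count, the false-positive chance is 16.5% to 31.6% for assumed correlations of 0.8 down to 0.3, and in 70% to 84% of those cases the GEC is not significant. If only the composites may count, it is 6.8% to 9.3%; if only the GEC, 5%. These figures rest on two-sided tests, 10 completers per sequence, equal correlations and a single time point.

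This should be fixed, but it does not invalidate the trial. The likely harm is an overstated efficacy conclusion from a pilot.

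**What to change.** Before unblinding, amend section 6.1 as follows:

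- Designate one BRIEF score at one time point as the sole primary test at 0.05, using the step 2 t-test on within-subject differences. The GEC T-score is the natural candidate because it is the plan's own overall composite.
- Have the investigators choose the time point, and reconcile section 1.6 B, section 6.1 and the schedules in section 1.3 with that choice.
- Replace the sentence dismissing Bonferroni with a statement that all other BRIEF scores and the secondary PDDBI scores are exploratory, reported as estimates with 95% confidence intervals and no significance claim.
- Only if significance claims on those scores are wanted, specify Holm or an adjustment that uses the correlation between scores, such as a permutation-based one.

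The cost is two or three sentences, with no new data, visits or participants. The downside is that fewer subscales can be called significant, and an effect confined to a few subscales may not show in the GEC. For that reason the score must be chosen before unblinding.
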